9.2. Clinical Laboratory Test Results

The laboratory test results will be summarized, for overall and by gender, by descriptive statistics at the scheduled visits, including the change from baseline and percent change from baseline for continuous results. For the continuous test results being classified into the three categories (low, normal, high) according to the normal ranges, the shift table from baseline to each post-baseline visit will be presented as well. When available, all the test results in the following table will be summarized.

Hematology:	Biochemistry:
Hemoglobin	Alanine transaminase
Platelets	Albumin
Total white blood cell count	Alkaline phosphatase
	Aspartate transaminase
Coagulation Profile:	Bilirubin (total)
Partial thromboplastin time (PTT)	Blood urea nitrogen
Prothrombin time (PrT)	Calcium

	Creatinine
Vitamin D	Creatine phosphokinase
	Cystatin c
Urinalysis:	Gamma-glutamyl transferase
Dipstick for presence of Blood	Glucose
Dipstick for presence of Glucose	Lactate dehydrogenase
Dipstick for presence of Ketones	Phosphate (inorganic)
Dipstick for presence of Protein	Potassium
	Sodium
	Total protein
	Uric acid

Note to programmers:

- Values in urinalysis (e.g. protein), spot urine test (protein to creatinine ratio UPCR), and chemistry (e.g. bilirubin) started with a '<' sign will be excluded from the analysis, but will be presented in listings with the '<' sign.
- Serum creatinine can be recorded in two units, µmol/L and mg/dL. In calculation of eGFR or summary of creatinine, the value in µmol/L needs to be converted to mg/dL using the following conversion formula: 1 mg/dL = 88.4 µmol/L.
- Serum creatinine can be entered in two fields in the SDTM (CHEMISTRY and ENZYME). When the results from same sample is entered at both fields, then the value is identical. In such cases, only one of them will be taken in the analysis.

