10.4. Urine Protein/Creatinine Ratio (UPCR)

UPCR will be classified into four categories. The 1st three are based on the Kidney Disease Improving Global Outcomes (KDIGO) guidelines:

- Normal to mildly increased: if $UPCR < 0.15$ gr/gr,
- Moderately increased: if $UPCR \geq 0.15$ gr/gr and ≤ 0.5 gr/gr, and
- Severely increased: if $UPCR > 0.5$ gr/gr
- PU (Protein Undetectable): in any case that UPCR is reported with a < sign. This happens in any case that the protein level is below the level of detection.

Urine protein/creatinine ratio (UPCR), by spot urine test, will be summarized at each visit based on the above 4 categories (Normal to mild increased; Moderately increased; Severely increased; PU) for overall population and by gender.

The shift of UPCR category from baseline to each of the post-treatment visit will be presented including number and percentage of patients. The percentage will be based on the number of patients in the respective baseline UPCR category.

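### The SAP 9.2 programming note drops every '<' laboratory result, which inflates chemistry visit means and percent high, and conflicts with the Protein Undetectable category for UPCR in SAP 10.4

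*SAP*

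**What the plan says.** SAP 9.2 plans by-visit descriptive statistics for laboratory tests, "including the change from baseline and percent change from baseline for continuous results". For results classed as low, normal or high, "the shift table from baseline to each post-baseline visit will be presented as well"; the biochemistry version is Table 14.3.4.1.2. The note to programmers under the test list then covers urinalysis values, "spot urine test (protein to creatinine ratio UPCR), and chemistry (e.g. bilirubin) started with a" less-than sign. These "sign will be excluded from the analysis, but will be presented in listings". Hematology is not named. SAP 7.2 allows no imputation of safety or efficacy values beyond its date rules and the adverse-event rules, so nothing replaces what is excluded.

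SAP 10.4 treats UPCR differently. Its fourth category is "PU (Protein Undetectable): in any case that UPCR is reported with a < sign". UPCR "will be summarized at each visit based on the above 4 categories", and the shift table uses the same categories: "The shift of UPCR category from baseline to each of the post-treatment visit will be presented including number and percentage of patients". The baseline table (SAP 8.3) and an eGFR-slope subgroup (SAP 10.1.3) both refer to the 10.4 categories. SAP 8.3 also has a binary proteinuria variable split at 0.5 g/g, with no stated rule for PU.

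**The concern.** A '<' result carries information: the value lies below a known limit. Excluding it removes results because they are low, so what remains is not representative. Change in clinical laboratory tests is a listed safety endpoint (SAP 3.2.1), and safety is the primary objective (SAP 3.1). Chemistry has no equivalent of the PU category.

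For UPCR the issue is that two sections give different instructions for the same result. SAP 2 ranks the SAP above the protocol, but nothing ranks 9.2 against 10.4. Read literally, 9.2 would take '<' UPCR results out of tables that 10.4 builds to include them.

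**Working it through.** The plan gives no figure to reproduce: no share of '<' results, detection limits or SDs are stated, and the 22 patients have no formal sample size calculation. The text comparison comes from the SAP; the distributions below are assumptions.

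**1. What the note reaches**

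| Result type | Planned summary | Effect of the 9.2 note |
|---|---|---|
| Chemistry (bilirubin is the example given) | Visit statistics, change, percent change, low/normal/high shift | '<' results lost from all of them |
| UPCR | Counts in four categories and a category shift (10.4); no mean planned in the SAP | Conflict: excluded by 9.2, kept as PU by 10.4 |
| Urinalysis | Dipstick tests; no shift table listed | Limited |
| Hematology | As for chemistry | Not named |

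**2. Visit mean.** Let the analyte be lognormal with log-scale SD s, let a fraction p of results lie below the limit, and let z_p be the standard normal p-quantile. Deletion multiplies the mean by Φ(s − z_p)/(1 − p).

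- p = 10% (z_p = −1.282): s = 0.5 gives Φ(1.782)/0.9 = 1.07; s = 1.0 gives Φ(2.282)/0.9 = 1.10.
- p = 20% (z_p = −0.842): Φ(1.342)/0.8 = 1.14; Φ(1.842)/0.8 = 1.21.
- p = 30% (z_p = −0.524): Φ(1.024)/0.7 = 1.21; Φ(1.524)/0.7 = 1.34.

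A simulation of 400,000 draws gives the same ratios. In that simulation, keeping '<L' at L/2 (L being the limit) gives 0.95 to 0.99 times the true mean for s = 0.5 and 0.99 to 1.00 times for s = 1.0. Substituting 0 and L gives outer bounds of 0.85 and 1.05 across these scenarios.

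**3. Percentage high.** With h high results among 22 patients and k '<' results excluded, the percentage moves from h/22 to h/(22 − k), if the denominator is the patients retained. With h = 4:

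- k = 0: 4/22 = 18.2%
- k = 2: 4/20 = 20.0%
- k = 4: 4/18 = 22.2%
- k = 7: 4/15 = 26.7%

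**4. Change from baseline.** Paired lognormal values were simulated with log-SD 1 and correlation 0.7, 20% of baseline values below the limit, and a pair deleted if either value is below it.

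| True log change | Log change in retained pairs | True mean raw change | Raw change in retained pairs |
|---|---|---|---|
| −0.40 | −0.32 | −0.55 | −0.71 |
| 0 | 0.00 | 0.00 | 0.00 |
| +0.40 | +0.34 | +0.81 | +0.95 |

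With no true change there is no bias: 8.7% of pairs are lost by moving from detectable to '<', and 8.7% by moving the other way. With a true change, the log change shrinks while the raw change grows. No single direction can be stated.

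**5. Baseline.** SAP 7.3 falls back to the last earlier assessment if Visit 1 is not available. Biochemistry and UPCR are also measured during screening. If an excluded '<' at Visit 1 counts as unavailable, an earlier detectable value would replace it; with the same limit, that value is higher. The SAP does not settle this.

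**The case against.** The best defence concerns UPCR. SAP 10.4 is the dedicated section, it assigns '<' results to PU without exception, and the category uses in 8.3 and 10.1.3 point to it. UPCR is not in the 9.2 test list, and the SAP plans no UPCR mean; protocol 10.5 did, but the SAP prevails. A sensible programmer could read 9.2 as meaning only that '<' results are not used as numbers. This largely stands. A reader might infer that the lowest-protein patients will be lost from the UPCR tables and the eGFR-slope subgroup; the cross-references to 10.4 do not support that. What remains is that 9.2 names UPCR, sets no such limit on its scope, and no sentence says which section governs.

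A reader might also infer that improvers disappear while worsening patients stay in, so that change and shift tables lean upward. The rule does not do that: a patient going from '<' to detectable is removed as well, and the bias in change depends on the statistic and the true change.

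Three further points are fair. The size cannot be known from the documents. The outputs are mainly descriptive, the '<' values stay visible in listings, and the planned paired t-test on eGFR slopes could be touched only through UPCR subgroup membership. And L/2 is one convention among several and would need an exception to 7.2. None of these removes the upward bias in chemistry visit means and percent high wherever '<' results occur.

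**Conclusion.** The concern holds for chemistry as a stated rule that discards known-low results. Visit means, and the percentage high among patients retained, are pushed upward. Patients with '<' at either visit drop out of the change and shift tables, unless 7.3 supplies another baseline. The illustrative inflation of the mean is 7% to 10%, 14% to 21% and 21% to 34% for 10%, 20% and 30% of results below the limit. This assumes a lognormal analyte with log-SD 0.5 to 1.0; no analyte in the documents is shown to reach these shares. An upward bias in the shift tables or in change from baseline is not established.

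For UPCR the defect is an unresolved conflict between 9.2 and 10.4. It costs no data if 10.4 governs. The note should be corrected, but the consequence is confined to mainly descriptive tables.

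**What to change.** Replace the note in SAP 9.2 with four statements.

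1. The exclusion does not apply to UPCR categories. A '<' UPCR result always goes to PU as in 10.4, including in 8.3 and 10.1.3. It counts as below 0.5 g/g in the binary proteinuria variable where the reported limit is below 0.5.
2. In low/normal/high shift tables, a '<L' result is classified by the category the limit implies and is not dropped.
3. For continuous chemistry summaries, report the number below the limit at each visit, and either the median with '<' results kept in rank order or a stated substitution (for example L/2, with 0 and L as sensitivity analyses) added as an exception to 7.2.
4. A '<' result at Visit 1 remains the baseline under 7.3.

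The cost is a few lines of SAP text and programming, with no new data. If means are kept, the price is accepting a simple substitution convention.

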9.3. Physical Examination

The physical examination results (normal / abnormal / not done) will be summarized by body system. Shift table by body system from baseline to each post-baseline visit will be presented as well. The tables will be presented for overall and by gender.

9.4. Electrocardiography (ECG)

Descriptive statistics of ECG parameters (quantitative) and assessments (qualitative) will be summarized for overall and by gender. The change and percent change from baseline will be summarized as well for ECG quantitative parameters. The shift from baseline will be presented for ECG qualitative assessments.

ECG parameters (quantitative)	ECG assessments (qualitative)
Mean Heart Rate	Rhythm – Normal Sinus Rhythm (NSR)
PR Interval, Aggregate	Conduction abnormalities
QRS Duration, Aggregate	Left ventricular hypertrophy
QT Interval, Aggregate	Supraventricular tachycardia
	Premature atrial contraction
	Atrial flutter
	Atrial fibrillation
	Premature ventricular contraction
	Ventricular tachycardia
	Any clinically abnormal findings (i.e. any abnormal condition as listed above)

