8. EFFICACY AND SAFETY ASSESSMENTS

8.1 Safety Variable(s)

- Safety will be assessed by the frequency, severity, and duration of treatment-emergent AEs (see Section 8.3, Adverse Events), including clinically significant laboratory abnormalities, ECG changes from baseline, physical examination findings and assessment of the injection site after administration of the study drug
- Anti-Drug (i.e., PRX-102) IgG antibodies will be assessed before dosing with PRX-102 at baseline (Visit 1). Anti-PRX IgG antibodies will be assessed every month for the first 6 months and every 3 months until the end of study through the last infusion. If a patient continues treatment in an extension study, the anti-drug antibodies will be assessed as part of that study. For patients who end treatment with PRX-102, anti-PRX-102 antibodies will be assessed 1 and 3 months after last infusion
- Anti-Drug IgE antibodies will be assessed in events of hypersensitivity reaction following Sponsor request
- Ability to taper off infusion premedication at the start of the study
- Requirement for use of premedication overall to manage infusion reactions

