3. OBJECTIVES AND ENDPOINTS

3.1. Objectives

The primary objective of this trial is to evaluate the safety of pegunigalsidase alfa in patients with Fabry disease currently treated with agalsidase alfa (Replagal®).

The secondary objective of this trial is to evaluate the efficacy of pegunigalsidase alfa in patients with Fabry disease currently treated with agalsidase alfa (Replagal®).

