3.2. Endpoints

3.2.1. Safety Endpoints

- Change from baseline in:
 - Clinical laboratory tests
 - Physical examination
 - Electrocardiogram
- Treatment-emergent adverse events
- Assessment of the injection site and infusion-related reactions (IRR), as part of the adverse events
- Ability to taper off infusion premedication after switch to pegunigalsidase alfa
- Requirement for use of premedication overall to manage infusion reactions
- Treatment-emergent anti-pegunigalsidase alfa antibodies

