4. STUDY DESIGN

This is an open label switch over study to assess the safety and efficacy of pegunigalsidase alfa in patients treated with agalsidase alfa (Replagal[®]) for at least 2 years and on a stable dose (>80% labelled dose/kg) for at least the last 6 months. Patients will be screened and evaluated over 3 months while continuing on agalsidase alfa. Following the screening period, patients will be enrolled and switched from their agalsidase alfa treatment to receive intravenous (IV) infusions of pegunigalsidase alfa 1 mg/kg every two weeks for 12 months. No more than 25% of treated patients will be female.

At the time of enrollment, premedication, if used for the agalsidase alfa infusions before enrollment, will be continued through the first infusion with pegunigalsidase alfa and then gradually tapered at the Investigator's discretion during the first 2 months of treatment. The first infusions of pegunigalsidase alfa will be administered under controlled conditions at the investigation site. The patient can receive pegunigalsidase alfa infusions in a home care setting once the Investigator and Sponsor Medical Director agree that it is safe to do so.

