4.1. Sample Size and Statistical Power Consideration

No formal sample size calculation has been performed for this study.

The sample size of 22 patients is adequate to evaluate the safety of switching from agalsidase alfa to pegunigalsidase alfa in this orphan disease in which patient recruitment in clinical trials is difficult.

4.2. Study Flow Chart:

Activity	Screening Period		Visits Treatment Period Pegunigalsidase alfa						
	Screening Visit (-3 Month)	Visit A (-2 Month) and B (-1 Month)	Visit 1	Visits 2, 4, 6, 8, 10, 12, 13, 15, 17, 19, 21, 23, 25, 26	Visits 3, 5, 9, 11	Visits 7, 20 (Months 3 and 9)	Visit 14 (Month 6)	Visits 16, 18, 22, 24	Visit 27 (Month 12)
Sign IC	x								
Assign screening number	x								
Medical history	x								
Demographics	x								
Alpha-galactosidase activity in plasma and leucocytes	x								
Historical serum creatinine	x								
Vital signs (blood pressure, pulse, temperature and respiration)	x		x	x	x	x	x	x	x
Body weight	x		x			x	x		x
Body height	x								
Physical examination	x		x			x	x		x
Concomitant medications (including pain and premedications)	x	x	x	x	x	x	x	x	x
Hematology	x		x			x	x		x
Biochemistry	x		x			x	x		x
Serum Creatinine and Cystatin C	x	x	x		x	x	x	x	x
Urinalysis – dipstick	x		x			x	x		x
Protein/Creatinine ratio spot urine test	x	x	x			x	x		x
HbsAg, HCV & HIV	x								
Serum pregnancy test (beta HCG)	x		x						
Urine Lyso Gb3 concentration	x		x			x	x		x
Plasma Lyso Gb3	x		x			x	x		x
Plasma Gb3	x		x			x	x		x

Activity	Screening Period		Visits Treatment Period Pegunigalsidase alfa						
	Screening Visit (-3 Month)	Visit A (-2 Month) and B (-1 Month)	Visit 1	Visits 2, 4, 6, 8, 10, 12, 13, 15, 17, 19, 21, 23, 25, 26	Visits 3, 5, 9, 11	Visits 7, 20 (Months 3 and 9)	Visit 14 (Month 6)	Visits 16, 18, 22, 24	Visit 27 (Month 12)
Anti-pegunigalsidase alfa Antibodies (IgG)			x		x	x	x		x
Electrocardiography (ECG)	x		x			x	x		x
Chest X-ray	x								
Cardiac function assessment (echocardiography and stress test)	x		x				x		x
Cardiac MRI			x				x		x
Inclusion/exclusion criteria	x								
Request for subject approval	x								
Enrollment approval		x ¹							
Mutation analysis			X						
PrT, PTT	X								
C3, C4	x								
Vit D	x								
Short Form Brief Pain Inventory (BPI)			x			x	x		x
Brain MRI			x						x
Mainz Severity Score Index (MSSI)			x				x		x
EQ-ED-5L			x				x		x
Pegunigalsidase alfa infusion + clinical observation			x	x	x	x	x	x	x
Adverse event assessments		x	x	x	x	x	x	x	x

1 After Visit B

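### SAP 9.4 summarises QT without correcting for heart rate, so the table cannot reliably separate a repolarisation change from a heart-rate change

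*SAP*

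**What the plan says.** Safety comes first in this study. SAP 3.1 states: "The primary objective of this trial is to evaluate the safety of pegunigalsidase alfa in patients with Fabry disease". SAP 3.2.1 names "Electrocardiogram" among the safety endpoints assessed as change from baseline, and Protocol 8.1 includes "ECG changes from baseline, physical examination findings and assessment of the injection site after administration of the study drug" among its safety variables.

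SAP 9.4 lists four quantitative ECG parameters: "Mean Heart Rate", PR, QRS and "QT Interval, Aggregate". The planned analysis is descriptive, and "The change and percent change from baseline will be summarized as well for ECG quantitative parameters". SAP 7.1 fixes the statistics as n, mean, standard error, standard deviation, median, minimum and maximum. The results go to Table 14.3.5.3.1.

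Neither document gives a rate-corrected QT, a correction formula, an RR interval or a QT threshold. The qualitative ECG list in SAP 9.4 has no item for QT prolongation, and its catch-all item covers only the conditions already listed.

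On timing, SAP 7.3 defines baseline as the Visit 1 assessment before the first infusion, or the last earlier assessment if that is missing. The flow charts place follow-up ECGs at Visits 7, 14, 20 and 27, all infusion visits. Protocol 9.1.6, 9.1.7 and 9.1.9 mark the antibody sample at these visits as taken before dosing but put no such mark on the ECG.

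**The concern.** The QT interval shortens as the heart beats faster. A change in uncorrected QT therefore mixes any drug effect on repolarisation with any change in heart rate between the two recordings.

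The design offers nothing to absorb a rate shift. SAP Section 4 says: "This is an open label switch over study to assess the safety and efficacy of pegunigalsidase alfa". With no concurrent arm, a drift in heart rate between baseline and follow-up goes straight into the mean QT change.

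Two errors are possible. A real prolongation accompanied by a faster heart rate could show as little or no change in raw QT. A slower heart rate alone could look like prolongation. Either would blur a named safety endpoint under the primary objective, even though both quantities needed for the correction are already on the ECG.

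**Working it through.** **Plan's own figure.** There is none to reproduce. The documents give no QT value, heart rate, variability or power figure for this endpoint, and SAP 4.1 says: "No formal sample size calculation has been performed for this study".

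**Inputs from the documents.** QT and heart rate are both listed in SAP 9.4; the planned sample is 22 (SAP 4.1).

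**Assumptions, not in the documents.** QTcF of 400 ms (range to 420), starting heart rate of 60 to 70 bpm (range 55 to 75), rate shifts of 3 to 10 bpm, and the Fridericia relation, with Bazett as a variant.

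**Formula.** QTcF = QT/(60/HR)^(1/3), so raw QT = QTcF × (60/HR)^(1/3).

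**Step 1: a rate change that mimics an effect.** Hold QTcF at 400 ms and start at 65 bpm.
- At 65 bpm: 400 × (60/65)^(1/3) = 389.5 ms.
- At 60 bpm: 400 × 1 = 400.0 ms, a change of +10.5 ms.
- At 70 bpm: 400 × (60/70)^(1/3) = 380.0 ms, a change of −9.5 ms.
- A rise of only 3 bpm gives −5.8 ms.

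Over QTcF 400 to 420 ms and 55 to 75 bpm, a fall of 5 bpm gives +8.6 to +14.0 ms and a rise of 5 bpm gives −7.9 to −12.4 ms. Under Bazett (exponent 1/2) at 400 ms and 65 bpm, the shifts are +15.7 and −14.0 ms.

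**Step 2: a rate change that hides an effect.** Let QTcF truly rise from 400 to 410 ms. Raw QT is unchanged when the new heart rate equals the old one × (410/400)^3 = old × 1.0769.
- From 60 bpm: a rise of 4.6 bpm.
- From 65 bpm: a rise of 5.0 bpm.
- From 70 bpm: a rise of 5.4 bpm.

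With a rise of 8 bpm, raw QT falls by 6.8, 5.4 and 4.3 ms respectively, despite the true increase of 10 ms.

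**Step 3: scale against sampling error.** With n = 22 and an assumed standard deviation of change of 10 to 20 ms, the 95% half-width is 2.08 × SD/√22, which is 4.4 to 8.9 ms. Under the Step 1 values at 65 bpm, a mean shift of 5 bpm moves mean raw QT by 9.5 to 10.5 ms, slightly more than the widest of these half-widths.

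**The case against.** The strongest reply is that heart rate sits beside QT in the same table, with its own change from baseline. If raw QT stayed at 400 ms while heart rate went from 60 to 70 bpm, QTcF would have risen to 400 × (70/60)^(1/3) = 421 ms. The table would show a QT change of 0 and a heart-rate change of +10 bpm, which should alert a careful reader. ECG data listings should also let QTcF be worked out by hand. A reader might infer that the plan hides a QT effect altogether, or that its QT table says nothing about repolarisation; for this reason, neither holds. What remains is that two separate sets of summary statistics do not correct each patient's value, and the largest QT change cannot be matched to that patient's heart-rate change.

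A reader might also infer that heart rate will differ between baseline and follow-up. The documents do not show this. Baseline is fixed as pre-infusion, only the later timing is open, and no observed heart-rate change is reported. Stress tests do not establish a difference either: they fall on Visits 1, 14 and 27, so on baseline as well as two of the follow-up visits.

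Three further points limit the weight of the concern. The summary is descriptive, with no test or decision rule attached. Protocol 8.1 also brings ECG changes into adverse-event assessment, and SAP 9.4 provides shift tables for ventricular tachycardia and conduction abnormalities. The early clinical experience summarised in Protocol Section 4 mentions no QT finding, so nothing here suggests a known QT problem with the product.

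Finally, the table shells are in a separate document (SAP Section 12) and could contain a corrected-QT row. The SAP's parameter list does not ask for one.

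**Conclusion.** The point holds as a reporting gap. SAP 9.4 plans change from baseline in uncorrected QT only, and that summary cannot reliably separate a repolarisation change from a heart-rate change.

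Under the assumed 400 ms and 60 to 70 bpm, a shift of about 5 bpm is enough to hide or mimic an effect of about 10 ms. That size depends on a mean rate shift actually occurring, and the documents neither report one nor rule one out.

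The gap does not invalidate the study and affects no type I error or power statement.

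**What to change.** In SAP 9.4, derive QTcF = QT/(60/heart rate)^(1/3) for each ECG from the two parameters already listed. Then:

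- Add QTcF and its change from baseline to Table 14.3.5.3.1, by visit, beside raw QT. Raw QT should stay, because SAP 7.5 says the final analysis will repeat the analyses in the interim study report, and dropping it would break that comparison.
- Add counts of patients by QTcF value and by increase from baseline. The documents contain no cut-offs, so the sponsor should prespecify them with a stated source.
- Flag ECGs with atrial fibrillation, paced rhythm or a conduction abnormality, and state how they enter the counts. SAP 9.4 already records atrial fibrillation and conduction abnormalities, and the MSSI in Protocol Appendix 5 records a pacemaker.
- State in the footnote or report whether the ECGs at Visits 7, 14, 20 and 27 were taken before or after the infusion, where this is known.

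The cost is one derived variable and a few table rows, with no new data collection. The downside is that QTcF is harder to interpret in the flagged ECGs, which is why they need their own rule.
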